3.1 Basic Information

3.1.1 Name, Components, Pharmacological Class

Allogeneic human islets of Langerhans are a cellular therapy product with systemic effect derived from the pancreas of a cadaveric donor.

3.1.2 Formulation

The product will be formulated in serum-free transplant media (indicator-free CMRL 1066 with HEPES, without Bicarbonate and supplemented with Human Albumin).

3.1.3 Route of Administration

The islets of Langerhans mixture will be delivered slowly into the portal vein via a syringe attached to a catheter hub or using an infusion bag. Access to the portal vein is achieved by transvenous or percutaneous transhepatic access under fluoroscopic and ultrasound guidance. If a transvenous technique is used, access to the right jugular vein is obtained using a Microstik needle under ultrasound guidance. A guiding sheath is advanced through the right atrium and into the right hepatic vein. Position is confirmed with injection of contrast medium.

3.1.4 Objectives and Planned Duration of Proposed Clinical Investigation

The primary objective of the study is to demonstrate the safety and efficacy of allogeneic islet transplantation in Type 1 diabetic patients performed at the University of Illinois at Chicago (UIC).

The purpose is to demonstrate that islet transplantation achieves better glycemic control than state-of-the-art insulin treatment in the management of Type 1 diabetic patients with brittle control and a history of severe hypoglycemic episodes with hypoglycemia unawareness. The expected duration of the entire proposed clinical trial is five years.

3.2 Non-US Regulatory Actions

In Canada, islet transplantation is approved and funded clinical care through the Province Wide Services of the Government of Alberta, and is also funded in selected provinces. Research protocols outside of clinical care are regulated through Health Canada.

4 General Investigational Plan

4.1 Background and Previous Human Experience

4.1.1 Type 1 Diabetes

Type 1 diabetes results from the body's failure to produce insulin, the hormone that "unlocks" the cells of the body, allowing glucose to enter and fuel them. It is estimated that 1.4 Mio of Americans have Type 1 diabetes. Although life expectancy of patients with Type 1 diabetes has much improved since the introduction of insulin therapy, chronic complications, including blindness and renal failure, are hampering the quality of life and represent a multi-billion dollar annual burden on the health care system of industrialized countries (2). Keeping blood glucose levels under tight control represents the most effective way either to prevent the onset or to reduce the progression of the chronic complications of Type 1 diabetes (3, 4). At present, such a goal may be accomplished by treating patients with intensified therapy regimens consisting of multiple insulin injections, which involve accurate blood glucose monitoring. However, administration of subcutaneous insulin can never approximate pulsatile insulin secretory patterns of the normal β -cell, and rarely attains normal blood glucose levels without the risk of major hypoglycemic episodes. In addition, intensive insulin therapy is only suitable for selected patients (5).

Pancreas transplantation is the only therapeutic modality which can stop the progression of diabetic complications (6) without increasing the incidence of hypoglycemic events (7). Unfortunately, this procedure, usually performed simultaneously with a kidney graft, has a high morbidity and a significant mortality rate (8). Pancreas transplantation, in spite of an important impact on the quality of life in successful cases (9), will be restricted to selected patients. In this context, islet transplantation appears to be the ideal solution, normalizing glucose metabolism without the risk of hypoglycemia (10) and avoiding the potentially life-threatening complications of whole pancreas grafts.

[figure not shown]
4.1.2 Allogeneic Islet Transplantation

A growing body of evidence over the past 15 years demonstrates that islet transplantation can restore insulin production and ameliorate glycemic instability in patients with Type 1 diabetes. From 1990 to 2001, more than 400 islet allotransplantations were reported to the International Islet Transplant Registry (ITR) (11). The last ITR analysis from 2001 reports sustained graft function (as defined by a basal C-peptide level of > 0.5 ng/mL or 0.17 nmol/L) at 1 month in 36% of patients who underwent transplantation from 1985 to 1989 and in 79% in transplant recipients from 1990-2000. Only 41% of the patients transplanted between 1990 and 2000 showed persistent graft function after one year. The rate of insulin independence remained very low with 20% of transplanted cases from 1990-2000 reaching insulin independence (11). At the time of writing, June 2009, the longest insulin-independence after allogeneic islet transplantation in a Type 1 diabetic patient reported to the registry exceeds 13 years (11, 12).

In North America from 1999-2005, thirty-one islet transplant programs conducted 592 allogeneic islet infusions (13). Increasing activity within islet transplant programs coincided with a breakthrough achieved by the Edmonton group that re-created enthusiasm for this approach among the medical and lay communities.

In the year 2000, the Edmonton group reported a series of seven consecutive patients reaching insulin-independence after transplantation of islets from multiple donors using a steroid-free, sirolimus-based immunosuppression (14). In contrast to previous series, in this report, non-uremic patients with brittle diabetes were chosen as recipients, and a minimum of 10,000 IEN/kg were infused per patient. By May 2003, 51 allogeneic islet transplantations had been performed at the University of Alberta in Edmonton. Overall patient survival was 100%. Insulin-free survival one and three years after islet transplantation was 79% and 50%, respectively, and 88% of patients presented with ongoing graft function at 3 years after transplantation. An intent to treat analysis comparing the outcome of islet and pancreas transplants (Figure 1) showed that levels of HbA1c remained within the normal range for the majority of patients during the 3-year follow-up period.

Figure 1 HbA1c before and after islet (a) and pancreas (b) transplantation. Presented as an intention to treat analysis with inclusion of patients with graft loss. The top, bottom, and line through the middle of the box correspond to the 75th percentile, 25th percentile, and 50th percentile respectively. The whiskers on the bottom extend from the 10th percentile and top 90th percentile. ■ represents the arithmetic mean. n represents the number of patients at the different follow-up time points

By November 2004, 65 patients had received islet transplantation through the Edmonton group. Forty-four patients completed the protocol to achieve insulin independence after 1-3 transplants. At 5-year follow-up, the majority (~ 80%) had C-peptide present, but only a minority (~ 10%) maintained insulin independence. The median duration of insulin independence was 15 months. HbA1c was well controlled in patients off insulin [6.4% (6.1-6.7)] and in those who resumed insulin and were C-peptide positive [6.7% (5.9-7.5)], and was higher in patients who lost all graft function [9% (6.7-9.3)]. Those who resumed insulin required half their pre-transplant daily dose. Post-transplant hypoglycemic scores improved significantly in both groups.

In 2005, the Minnesota group reported results of a 1-year prospective follow-up trial in which all eight subjects achieved insulin independence and freedom from hypoglycemia after single-donor, marginal-dose islet transplantation. Five recipients remained insulin-independent for longer than one year. Investigators related improved islet engraftment to peritransplant administration of the soluble tumor necrosis factor receptor etanercept. Tumor necrosis factor alpha is cytotoxic to human beta cells, and its selective inhibition in murine models has promoted reversal of diabetes after marginal-mass islet transplants (26).

In 2006, Shapiro et al. (15) reported results of a multinational prospective trial conducted at six centers in North America and three in Europe to explore the feasibility of reproducing the Edmonton protocol. The trial was a collaboration by the National Institutes of Health and the Immune Tolerance Network with a goal to establish centers of excellence to conduct future tolerance-based trials. The protocol standardized pancreas selection, islet processing, product-release criteria, recipient selection, and post-transplantation care. At the nine centers, 36 subjects received a total of 77 islet infusions. Forty-four percent reached the primary endpoint of insulin independence defined as HbA1c less than 6.5%, a glucose level after overnight fast not exceeding 140 mg/dL more than three times per week, and a 2-hour postprandial glucose level not exceeding 180 dL more than four times per week. By two years post transplant, 76% had become insulin dependent. C-peptide was detectable in 70% of subjects, and all subjects with residual islet function were protected against severe hypoglycemia and hyperglycemia. Investigators observed that previous experience at each site significantly affected achievement of the primary endpoint, and regionalization of islet processing centers could potentially reduce costs and improve outcomes. This trial demonstrated that islet transplantation performed by the Edmonton protocol can restore long-term endogenous insulin production and glycemic stability. Although insulin independence was not sustained, persistent islet function protected recipients from severe hypoglycemia and improved HbA1c levels.

4.1.3 Allogeneic Islet Transplantation at the University of Illinois (16)

During an initial Phase 1/2 study, we demonstrated safety and efficacy of islet transplantation at the University of Illinois and reported data to the Food and Drug Administration (FDA). The sample consisted of 10 adults with brittle Type 1 diabetes defined as metabolic lability despite optimal insulin management efforts. Subjects presented with hypoglycemic unawareness and normal kidney function, and met all enrollment criteria. In this section we summarize study results.

Subjects comprised two groups. Group 1 (n = 4) received the Edmonton protocol. Group 2 (n = 6) received the Edmonton protocol and additionally the soluble tumor necrosis factor receptor antagonist etanercept and the incretin analog exenatide. Subjects in Group 1 and 2 had similar age distribution (49.2 ± 11.3 and 44.8 ± 10.0 years, $p = 0.5$), diabetes duration (30.2 ± 9.2 and 27 ± 10.8 years, $p = > 0.5$), body weight (61.0 ± 4.3 and 63.8 ± 5.3 kg, $p = 0.5$) and pre-transplant insulin requirements (39.3 ± 2.9 and 32.1 ± 8.6 U/day, $p = 0.5$).

The 10 subjects received 18 islet transplants. Subjects in Group 1 received a mean total number of islets (EIN) of $1,460,080 \pm 418,330$ in 2 ($n = 2$) or 3 ($n = 2$) islet infusions. Subjects in Group 2 received a mean total EIN of $756,354 \pm 180,755$ in 1 ($n = 4$) or 2 ($n = 2$) islet infusions.

All subjects had adverse events or experiences comparable to the types and rates reported by other centers. No patient died. No IND safety reports were required. No subjects experienced life-threatening adverse events during transplantation procedures. And no subject withdrew because of adverse experiences, dissatisfaction with the study, or for any other reason.

In Group 1, 2 subjects became insulin independent after two islet transplants, and 2 subjects became insulin independent after three transplants. All subjects in Group 1 completed 64 weeks of post-transplant evaluation and began a 5-year follow-up schedule.

study, namely to develop a data base for future trials investigating strategies to improve outcomes of allogeneic islet transplantation in diabetic patients. Such an improvement has already been achieved by adding exenatide and etanercept to the treatment of islet recipients in Group 2.

From our study we learned first, that the quality of the islet preparation is of utmost importance to achieve consistent graft function, and that UIC has the necessary know-how to produce such islet grafts. Secondly, we learned that islet graft function can be improved by pharmacological means, by achieving insulin independence with fewer islets when using a potent anti-inflammatory drug and an incretin analog. Therefore, we propose a Phase 3 study to demonstrate the efficacy of islet transplantation at University of Illinois at Chicago.

4.2 Indication to be Studied

Enrolling subjects must have Type 1 diabetes mellitus for more than 5 years, present with normal kidney function and have metabolic lability despite optimal intensive insulin management efforts. The enrollment inclusion and exclusion criteria for recipients and donors are discussed in more detail in Section 6.4 *Study Population*.

4.3 General Approach in Evaluation of the Product

4.3.1 Rational for Proposed Clinical Trial

Allogeneic islet transplantation is still considered an experimental procedure and can only be performed under an investigational plan reviewed by the FDA. The Edmonton protocol is currently the only protocol that has shown an acceptable safety and efficacy profile in a larger number of patients receiving allogeneic islet transplants (10, 17). The investigators have shown in a phase 1/2 trial at UIC the safety of the islet preparation, the procedure, and medical treatment. Therefore, the investigators propose this Phase 3 clinical trial protocol testing the safety and efficacy of allogeneic islet transplantation in Type 1 diabetic patients performed at the University of Illinois at Chicago.

4.3.2 General Approach for the Evaluation of the Study

The primary goal of this exploratory study is to demonstrate the safety and efficacy of allogeneic islet transplantation performed at the University of Illinois at Chicago. The study will collect safety and efficacy data from the islet isolation, the transplantation procedure, and the medical treatment during the one-year follow-up period after completion of the first and last islet transplant.

4.4 Trial Type and Number of Subjects to be Enrolled

The protocol presented herein is a Phase 3 clinical trial. It is a single center, open label, prospective trial in which 1-3 allogeneic pancreatic islet transplants per subject will be applied to a total of at least 50 study participants at the University of Illinois at Chicago. We plan to recruit 55 subjects and anticipate 10% attrition. A sample size of 50 subjects, will achieve sufficient power to conduct the proposed statistical analyses. For endpoint definitions and power analysis, please refer to Section 6.11 *Assessment of Endpoints*.

	LDL elevation	Possibly	2/10 (20)
	Triglycerides elevation	Possibly	2/10 (20)
	Hypophosphotemia	Possibly	4/10 (40)
	Hypomagnesemia	Possibly	6/10 (60)
	Hypoglycemia on exenatide	Possibly	3/10 (30)
	Weight loss	Possibly	10/10 (100)
Hematologic	Anemia	Possibly	10/10 (100)
	Leukopenia	Possibly	10/10 (100)
	Neutropenia	Possibly	7/10 (70)
	Platelet elevation	Possibly	5/10 (50)
	Thrombocytopenia	Possibly	4/10 (40)
Renal	Creatinine elevation	Possibly	3/10 (30)
	Renal failure, acute	Possibly	1/10 (10)
Infections	C-difficile	Possibly	1/10 (10)

Category	Adverse Events / Experiences	Related to Research	Total Subjects (%)
	CMV seroconversion	Possibly	2/10 (20)
	Osteomyelitis	Possibly	2/10 (20)
	Upper respiratory infection	Possibly	5/10 (50)
	Bronchitis	Possibly	2/10 (20)
	Pneumonia	Possibly	1/10 (10)
	Urinary tract infection	Possibly	5/10 (50)
	Viral stomatitis	Possibly	1/10 (10)
	Dental infection	Possibly	3/10 (30)
	Otitis media	Possibly	3/10 (30)
	Sinusitis	Possibly	2/10 (20)
	Influenza	Possibly	4/10 (40)
	Candida oral infection	Possibly	3/10 (30)
	Herpes zoster	Possibly	2/10 (20)

5 (Investigator brochure)

Not applicable

6 Protocol

6.1 Introduction

The replacement of insulin producing beta cells by islet transplantation has been shown to effectively control blood glucose levels in individuals with Type 1 diabetes. While the concept of islet transplantation is simple, its widespread clinical application has been hampered by a variety of technical and biological obstacles. Clinical trials from 1980 to 1998 in patients with juvenile diabetes had limited success, but showed that restoration of endogenous insulin secretion and, in some cases, even insulin independence was achievable through implantation of isolated islets (18-24). However, the variable and unpredictable outcome hindered the entry of islet transplantation to clinical reality. More recently, the successful clinical trials in islet transplantation in non-uremic Type 1 diabetic patients by the Edmonton group (14), focused much attention on the treatment of diabetes by islet transplantation. A more detailed review of previous and current experience with human islet transplantation is outlined in Section 9 *Previous Human Experience with the Investigational Drugs*

Before islet transplantation could become standard medical care, the results obtained by the Edmonton group had to be reproduced by other centers. Our own Phase 1/2 trial has reproduced those results and now requires a larger trial that, if confirming the results, may confer the possibility for a biological license application to make islet transplantation an accepted medical treatment to treat brittle Type 1 diabetic patients. In addition, this would facilitate longer and larger clinical trials to further improve the procedure.

6.2 Objective and Purpose of the Study

The primary objective of this study is to demonstrate the safety and efficacy of allogeneic islet transplantation in Type 1 diabetic patients performed at the University of Illinois at Chicago (UIC).

The purpose is to demonstrate that islet transplantation achieves better glycemic control than state-of-the-art insulin treatment in the management of Type 1 diabetic patients with brittle control and a history of severe hypoglycemic episodes with hypoglycemia unawareness. The series of transplants performed with the protocol described herein will provide the base for a biological license application in islet transplantation.

6.3 Study Design

The herein presented protocol is a Phase 3 study. It is a single center, open label trial in which 1-3 allogeneic pancreatic islet transplants per subject will be applied to a total of at least 50 study participants at the University of Illinois at Chicago

6.4 Study Population

This protocol is designed as a limited series of islet transplants for at least 50 Type 1 diabetic adult subjects considered to have brittle diabetes for which glycemic control using insulin is problematic if not impossible. The enrollment inclusion and exclusion criteria for recipients and donors are given below.

6.4.1 Recipient Inclusion Criteria

Enrolling subjects must have Type 1 diabetes mellitus for more than 5 years, complicated by the following situations that persist despite intensive insulin management efforts (Appendix *Pre-Screening*):

- a. At least one episode of severe hypoglycemia in the past 3 years defined as an event with symptoms compatible with hypoglycemia in which the subject required the assistance of another person, and which was associated with either a blood glucose level < 50 mg/dL (2.8 mmol/L) or prompt recovery after oral carbohydrate, intravenous glucose, or glucagon administration
- b. Reduced awareness of hypoglycemia, as defined by the absence of adequate autonomic symptoms at capillary glucose levels of < 54 mg/dL (3 mmol/L as reported by the subject

6.4.2 Recipient Exclusion Criteria

Subjects will be excluded from the study if one of the following conditions is present:

1. Diagnosis of co-existing cardiac disease, characterized by any one of these conditions:
 - a. Recent myocardial infarction (within past six months), or
 - b. Angiographic evidence of non-correctable coronary artery disease, or
 - c. Evidence of ischemia on functional cardiac exam (with a stress echo test recommended for subjects with a history of ischemic disease).
 - d. Heart failure > New York Heart Association II
2. Active alcohol or substance abuse includes cigarette smoking (must be abstinent for six months). Active alcohol abuse should be considered using the current National Institute on Alcohol Abuse and Alcoholism definitions.
3. Psychiatric disorder making the subject not a suitable candidate for transplantation, e.g., schizophrenia, bipolar disorder, or major depression that is unstable or uncontrolled on current medication. (A psychological or psychiatric consultation is required only if considered necessary by some current indication or history.)
4. History of non-adherence to prescribed regimens
5. Active infection including hepatitis C, hepatitis B, HIV
6. TB (by history or currently infected as evidenced by a positive QuantiFERON® - TB Gold test or under treatment for suspected TB)
7. Any history of malignancies except squamous or basal skin cancer. Any subject found to have squamous or basal cancer is required to have it removed prior to transplant.

8. Known family history of MEN2 or MCT
9. History of stroke within the past 6 months
10. BMI > 27 kg/m²
11. C-peptide response to glucagon stimulation (1 mg iv) (any C-peptide ≥ 0.3 ng/mL)
12. Inability to provide informed consent
13. Age less than 18 or greater than 75 years
14. Creatinine clearance < 80 mL/min/1.73 m² by 24-hour urine collection. If corrected creatinine clearance is < 80 and serum creatinine is < 1.2 mg/dL, then a nuclear renal scan is required to determine glomerular filtration rate.
15. Serum creatinine consistently > 1.5 mg/dL
16. Macroalbuminuria (urinary albumin excretion rate > 300 mg/24h)
17. Baseline Hb < 12 gm/dL in women or < 13 gm/dL in men
18. Baseline liver function tests (LFT) outside of normal range (An initial LFT test panel with any values > 1.5 times normal upper limits will exclude a subject without a re-test. A re-test for any values between normal and 1.5 times normal should be made, and if the values remain elevated above normal limits, the subject will be excluded.)
19. Untreated proliferative retinopathy
20. Positive pregnancy test, intent for future pregnancy, or male subjects' intent to procreate, unwilling to follow effective contraceptive measures, or presently breast-feeding
21. Previous transplant (except islet transplant), or evidence of hyper sensitization on PRA (determined by demonstration of positive results for anti-HLA antibodies using solid phase immunoassay with soluble HLA Class I molecules as a target, or a general PRA panel with reactivity > 80%). All subjects require a negative crossmatch with the donor before transplant (UNOS requirement).
22. Insulin requirement > 0.7 IU/kg/day
23. HbA1c > 12%
24. Hyperlipidemia (fasting LDL cholesterol > 130 mg/dL, treated or untreated, and/or fasting triglycerides > 200 mg/dL)
25. Under treatment for a medical condition requiring chronic use of steroids
26. Use of Coumadin or other antiplatelet or anticoagulant therapy, or subject with PT-INR > 1.5. Low dose aspirin is allowed after transplantation.
27. History of Factor V deficiency
28. Currently smoking tobacco
29. Addison's disease
30. Symptomatic cholecystolithiasis
31. Acute or chronic pancreatitis
32. Symptomatic peptic ulcer disease
33. Severe unremitting diarrhea, vomiting, or other gastrointestinal disorders that could interfere with the ability to absorb oral medications
34. Treatment with antidiabetic medication other than insulin within 4 weeks of enrollment
35. Use of any study medication within 4 weeks of enrollment
36. Received live attenuated vaccine(s) within 2 months of enrollment

37. Any medical condition that, in the opinion of the investigator, might interfere with safe participation

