6.9 Adverse Events Definitions and Monitoring

6.9.1 Adverse Event (AE)

An adverse event is any unfavorable and unintended diagnosis, symptom, sign (including an abnormal laboratory finding), syndrome, or disease which either occurs during the study, having been absent at baseline, or if present at baseline, appears to worsen.

The length of time between screening and first transplantation may be 6 months or more. Therefore, non-serious adverse events will be recorded on the case report forms (CRF) for the period starting with hospitalization for the first transplantation and during the subsequent study period because these events are relevant to the islet cell transplantation. All serious adverse events (see below) regardless of time relative to transplantation will be recorded on the case report form

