9.3.6 Immunizations

Influenza Vaccine

Subjects will be asked to obtain influenza virus vaccine from a primary care provider or community flu vaccine program annually in the fall or winter in accord with current CDC recommendations for patients with diabetes or immunocompromising conditions caused by medications, and also in accord with the American Diabetes Association Standards of Medical Care in Diabetes - 2008.

Pneumococcal Vaccine

Subjects will be asked to obtain at least one pneumococcal vaccine in accord with current CDC recommendations for patients with diabetes or immunocompromising conditions, and also in accord with the American Diabetes Association Standards of Medical Care in Diabetes - 2008. CDC recommends a one-time revaccination if the vaccine was administered > 5 years ago.

Hepatitis Vaccine

Subjects will be asked to obtain a series of hepatitis B vaccine in advance of transplant in accord with current Centers for Disease Control (CDC) recommendations for patients with diabetes or immunocompromising conditions.

10 Additional Information

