## **8.2. Analysis of Baseline Data**

### **8.2.1 Analysis of demographic variables**

Age will be reported in years and calculated using the formula  $\text{Age} = (\text{date of the islet transplant} - \text{the date of birth}) / 365.25$  and will be rounded to one decimal place. In the case when no transplant is done, the age at enrollment (calculated using the date of Informed Consent instead) will be used for baseline. The distribution of age at baseline will be displayed as mean, standard deviation, median, minimum and maximum.

Sex, race and ethnicity will be tabulated and counts and percents will be displayed.

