### **8.2.3 Analysis of baseline diabetes control variables**

The diabetes control variables are all continuous scale variables and will be summarized as mean, standard deviation, median, minimum and maximum.

Insulin requirement will be taken from self-reported insulin regimen on the current medication list at the point of immediate pre-transplant assessment. If a range instead of an exact dose schedule is given, the average value of the range will be used. Insulin dosing will be summarized in total units per kg per day by administration routes. If the insulin doses are

reported as units per day, the value will be divided by the patient weight (in kg) measured at the corresponding visit to derive the requirement in units/kg/day.

Reduced awareness of hypoglycemia is reported qualitatively at enrollment. The proportion of patients having reduced awareness of hypoglycemia at baseline will be summarized.

Baseline SHE frequencies will be based on records available during the time period between study enrollment and the first islet transplant. A SHE is identified as a hypoglycemic event in which the patient required assistance, including help from someone else to recognize or treat the reaction, injection of Glucagon, or use of hospital/ambulance. Additionally, either a blood glucose (BG) level under 50 mg/dL (when recorded) or recovery with juice/food/glucagon is concomitant of a SHE.

The frequency of SHE is calculated by dividing the total number of SHE by the total number of days during which the events were recorded and then multiplied by 30 to produce incidence per month. Note that the duration of time between enrollment and the first transplant may vary by patient. The frequencies of SHE will be summarized at baseline.

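### Exclusion items 34-36 are counted from enrollment, but first exposure comes at transplant, which may be 6 months or more later, and no available text re-applies them before the first infusion

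*Protocol*

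**What the plan says.** Protocol section 6.4.2 ties three exclusions to enrollment:

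- item 34: "Treatment with antidiabetic medication other than insulin within 4 weeks of enrollment"
- item 35: "Use of any study medication within 4 weeks of enrollment"
- item 36: "Received live attenuated vaccine(s) within 2 months of enrollment"

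The protocol does not define enrollment. SAP section 8.2.1, for a patient who is never transplanted, uses "the age at enrollment (calculated using the date of Informed Consent instead". SAP section 8.2.3 places enrollment before the first transplant and notes that "the duration of time between enrollment and the first transplant may vary by patient".

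Under protocol section 6.6.2, the exclusion list is applied before a subject joins the waiting list. Immunosuppression (6.5.2) and exenatide (6.5.3) begin with the first transplant. On the interval between, section 6.9.1 states: "The length of time between screening and first transplantation may be 6 months or more".

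On baseline, SAP section 8.2.3 states: "Baseline SHE frequencies will be based on records available during the time period between study enrollment and the first islet transplant". The baseline HYPO score uses the same interval, capped at the 365 days before the first infusion. Baseline HbA1c is the immediate pre-transplant result or, failing that, the last screening result.

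**The concern.** A washout or vaccine window does its work at the moment of exposure. Here it is fixed to an earlier date, and the protocol itself expects a long and variable wait between the two. Followed exactly, the text lets a subject receive a live vaccine, or start a non-insulin antidiabetic drug, shortly before induction without breaching items 34-36.

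Two things are at stake. The first and more important is subject safety, through a live vaccine given before T-cell-directed induction. The second is descriptive. The study's purpose takes insulin treatment as its reference, and baseline HYPO, severe hypoglycemic event (SHE) frequency and HbA1c all come from the wait. Non-insulin drug use in that period would enter these baselines, and with them the HYPO percent reduction (Table 14.2.2b) and the HbA1c-change display (Figure 14.2.1).

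**Working it through.** The plan gives no figure to reproduce here; sample size, power and alpha play no part. The check compares window length and anchor with the wait, and then looks for any re-check.

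**Inputs.** Window X is 28 days for items 34-35 and 2 months for item 36 (section 6.4.2). With one month taken as 30.44 days, 2 months is about 61 days. The wait G is given only as possibly 6 months or more (section 6.9.1), without a median or range, so G is an assumption and is varied from 1 to 12 months.

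**Two readings of the windows.** If a window covers only the X days before enrollment, all G days of the wait are uncovered. If it covers X days on either side, uncovered days = max(0, G − X).

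**Two-sided reading, days of the wait left uncovered:**

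| Wait G | Items 34-35 (X = 28) | Item 36 (X = 61) |
|---|---|---|
| 1 month (30 d) | 2 | 0 |
| 2 months (61 d) | 33 | 0 |
| 3 months (91 d) | 63 | 30 |
| 6 months (183 d) | 155 (155/183 = 85%) | 122 (122/183 = 67%) |
| 12 months (365 d) | 337 | 304 |

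**Is the period just before transplant covered?** Under the two-sided reading the windows end on day 28 and day 61 after enrollment. At G = 183, the last 4 weeks start on day 183 − 28 = 155 and the last 2 months on day 183 − 61 = 122. Both come after the window has closed, so neither period is covered at all. In general this happens once G is at least 2X: 56 days for items 34-35 and about 122 days for item 36. With a short wait (up to about 4 weeks, or 2 months for item 36) the two-sided windows still reach the transplant.

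**Share of the HYPO baseline inside the 4-week window after enrollment.** 28/365 = 8% for a full 365-day baseline, and 28/183 = 15% for a 6-month wait. The share rises as the wait shortens.

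**Is there a re-check before the first infusion?**

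- Section 6.6.3 repeats HbA1c, metabolic panel, microalbumin/creatinine ratio and PRA every 3 months, with history, examination, ECG and further laboratory tests if there is no transplant by 6 months. It does not name vaccines, non-insulin antidiabetic drugs or study medication.
- Section 6.6.4 (immediate pre-transplant work-up) lists history, examination and laboratory tests for medical fitness. Items 34-36 are not named.
- Section 6.5.1 makes absence of exclusion criteria a condition for retransplantation or a fourth infusion. No matching sentence covers the first.
- Section 6.11.2 has the Data Monitoring Committee review eligibility about 2 weeks after each transplant, too late to prevent exposure.

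**Would the SAP show non-insulin drug use during the wait?** Only in part. Under SAP section 8.2.4, Table 14.1.7 counts drugs still ongoing at the last visit before the first transplant. A drug started and stopped during the wait does not appear there.

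**The case against.** Several checks already exist. Section 6.5.1 speaks of admitting an eligible subject. A history is taken at admission to confirm fitness. Item 37 allows exclusion for any medical condition that might interfere with safe participation. SAP section 8.2.3 refers to a current medication list at the pre-transplant assessment. The Detailed Visit Schedule and Transplant Order appendices appear only as headings, and the content of the Study Continuation Record page (SAP section 6) is not given. A re-check could sit in any of these. This stands as a limit on the finding: a case may well be caught, but nothing available says that items 34-36 are re-applied.

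Four stronger readings are tempting and do not hold.

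- A reader might infer that waits are usually long. Section 6.9.1 says only that they may be, and gives no frequency.
- A reader might infer that subjects have no protection at transplant. The checks above rule that out.
- A reader might infer that the protocol sends subjects for live vaccines, since section 9.3.6 says "Subjects will be asked to obtain influenza virus vaccine from a primary care provider or community flu vaccine program annually". That section ties influenza, pneumococcal and hepatitis B vaccination to CDC recommendations, whose content cannot be judged from these documents. What remains is a live vaccine that a subject obtains during the wait.
- A reader might infer that the efficacy result is biased. The primary endpoint is a post-transplant proportion with no baseline term (SAP section 9.1). The SAP's insulin-treatment reference rates are external (0.3% in section 2.7.2, below 1% in section 2.8). SAP section 9.2 states no hypotheses beyond the primary analyses, and baseline CGMS is taken at screening. Contamination of the other baselines is possible, not shown. That item 34 was meant to protect the baseline is also an inference; the protocol gives no reason for it.

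**Conclusion.** The concern holds in limited form. Items 34-36 are fixed to enrollment, exposure begins at the first transplant, and no available text carries the items across the wait. At a 6-month wait the sponsor's own 4-week and 2-month periods immediately before exposure fall entirely outside the written windows under either reading. With short waits and a two-sided reading they may still be covered. The conclusion assumes that enrollment means informed consent, as the SAP uses it, and that the unavailable appendices and CRF page contain no explicit re-check.

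The main consequence is a safety gap in the wording of item 36. The consequence for analysis is small: it reaches only descriptive baseline HbA1c, SHE and HYPO values and the change displays built on HbA1c and HYPO. The primary endpoint and its confidence interval are untouched. Because the gap is in the rule itself and is cheap to close, it should be corrected.

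**What to change.** In the protocol, define enrollment. Reconcile sections 6.4.2, 6.5.1, 6.6.4 and 6.9.1 so that the sponsor's own items 34-36 are also verified at the pre-transplant admission, against the start of study drug. One checklist line, answered from the history already taken there, is enough. State whether study medication in item 35 means this trial's drugs or any investigational drug. The window lengths, and how a subject found inside a window is handled on the waiting list, are for the sponsor to decide. If an appendix or the Study Continuation Record already contains the re-check, a cross-reference from section 6.4.2 would suffice.

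In the SAP, flag baseline HbA1c, SHE and HYPO values from any subject who used a non-insulin antidiabetic drug at any time between enrollment and first transplant, since Table 14.1.7 cannot identify all of them.

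The cost is amendment wording, one checklist line and one derived flag. The downside is that an occasional subject may miss an organ offer.
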